2.5 Measurements

Table 2. Summarization of measures used for the protocol, “The Combined Effects of Prolonged Sitting and Mental Stress on Vascular and Cerebrovascular Function in Middle-Aged Adults”. Each experimental variable is listed under the “Outcomes” column with its designation as either a primary, secondary, or mechanistic measure listed under the “Role Classification” column. The “Device” column names the equipment used to collect the data. **Abbreviations:** TCD, Transcranial Doppler; CON, Control condition; SMS, Sitting mental stress condition; VFT, Verbal fluency test; TMT, Trail making test; NIRS, Near-infrared spectroscopy; cwNIRS-SRS, Continuous-wave near-infrared spectroscopy. Minute values are expressed relative to the administration of the MAT.

Outcomes	Device	Unit	Time Period (min)			Role Classification
			Condition	Time Periods (min)	Measurements Taken	
Brain Pulse Wave Velocity	TCD	meters per second (m/s)	CON	Continuous	1	Primary
			SMS	Continuous	1	
Brachial-femoral Pulse Wave Velocity (PWV)	VICORDER®	meters per second (m/s)	CON	-5, 0, 5, 10, 15, 20, 25	7	Primary
			SMS	-115, -15, 0, 5, 10, 15, 20, 25	8	
Executive Function	VFT/ TMT	Cognitive performance: measured in seconds (s)	CON	25	1	Secondary
			SMS	25	1	
Neurovascular Coupling	NIRS/ TCD	Unitless: relationship between local neural activity and subsequent changes in cerebral blood flow. [CITE]	CON	Continuous	1	Secondary
			SMS	Continuous	1	
Augmentation Index (Aix)	VICORDER®	Percentage. It is defined as the difference between the second and first systolic peaks (P2-P1) expressed as a percentage of the pulse pressure ^{24,25}	CON	-5, 0, 5, 10, 15, 20, 25	7	Secondary
			SMS	-115, -15 0, 5, 10, 15, 20, 25	8	
Carotid-femoral PWV	VICORDER®	meters per second (m/s)	CON	-5, 25	2	Secondary
			SMS	-115, -15, 25	3	
Central Blood Pressures (CBP)	VICORDER®	Millimeters of Mercury (mmHg)	CON	-5, 0, 5, 10, 15, 20, 25	7	Secondary
			SMS	-115, -15 0, 5, 10, 15, 20, 25	8	
Femoral-ankle PWV	VICORDER®	meters per second (m/s)	CON	-5, 25	2	Secondary
			SMS	-115, -15, 25	3	
Physical Activity	ActiGraph	Minutes. Activity data will be classified as either "Light", "Moderate", or "Vigorous".	CON	Continuous	1	Mechanistic
			SMS	Continuous	1	
Sleep Duration	ActiGraph	Minutes.	CON	Continuous	1	Mechanistic
			SMS	Continuous	1	
Cerebral Perfusion	cwNIRS-SRS	Relative changes in total hemoglobin concentration (tHb). Expressed as a percentage.	CON	Continuous	1	Mechanistic
			SMS	Continuous	1	
Cerebrovascular Blood Flow	Doppler Ultrasound	meters per second (m/s)	CON	-5, 20	2	Mechanistic
			SMS	-120, -5, 20	3	
Middle Cerebral Artery Velocity	TCD	Centimeters per second (cm/s)	CON	Continuous	1	Mechanistic
			SMS	Continuous	1	
Static Cerebral Autoregulation	TCD	Unitless. Refers to MAP and CBF under steady state conditions that can be observed over a period of time ²⁶	CON	Continuous	1	Mechanistic
			SMS	Continuous	1	
Baroreflex Sensitivity	NIBP	Sensitivity: BRS is defined as the change in heart rate variability in milliseconds per unit change in BP	CON	Continuous	1	Mechanistic
			SMS	Continuous	1	
Heart Rate Variability (HRV)	NIBP	milliseconds (ms)	CON	Continuous	1	Mechanistic
			SMS	Continuous	1	
Heart Rate	NIBP	Beats per minute	CON	Continuous	1	Mechanistic
			SMS	Continuous	1	
Peripheral blood pressures (SBP, DBP)	VICORDER®	Millimeters of Mercury (mmHg)	CON	-5, 0, 5, 10, 15, 20, 25	7	Mechanistic
			SMS	-115, -15 0, 5, 10, 15, 20, 25	8	
Tissue Saturation Index	cwNIRS-SRS	Relative changes in TSI. Data will be presented as percent changes.	CON	Continuous	1	Mechanistic
			SMS	Continuous	1	
Venous Pooling in the Gastrocnemius	cwNIRS-SRS	This is a physiological response to prolonged sitting. It is quantified using the NIRS-SRS device by recording levels of tHb at the gastrocnemius	CON	Continuous	1	Mechanistic
			SMS	Continuous	1	

DEVICE 1: VICORDER®

PWV is calculated by dividing arterial path length (L) by the pulse transit time (TT) between a proximal and distal arterial segment. Measurements for L are acquired by recording the straight line distance between the proximal and distal cuff, per manufacturer guidelines. For PWV measures including the carotid artery, the straight line distance from the carotid artery to the sternal notch is included in calculations for L.

Transit time is calculated by the Vicorder software's proprietary algorithm that measures the time between the foot of the proximal pressure waveform to the foot of the distal pressure waveform. Pressure waveforms will be simultaneously captured using volume displacement cuffs. A small balloon cuff is placed over the carotid artery. The balloon used to generate the carotid pulse wave does not cause discomfort as it inflates to sub-diastolic blood pressure (~50 mmHg).

DEVICE 2: Transcranial Doppler

Brain PWV and Middle cerebral artery velocity (MCAv) will be measured using continuous bilateral TCD (ST3, Spencer Technologies). MCAv accounts for 70-80% of the brain's total perfusion²⁵. The data will be acquired continuously (50 Hz) using an analog-to digital convertor (PowerLab 30, ADInstruments).

DEVICE 3: Non-Invasive Blood Pressure (NIBP)

The PowerLab data acquisition system (PowerLab 30 series, ADInstruments, CO, USA) will be used to simultaneously acquire signals from each device and from ECG. A standard Lead II ECG will be recorded from three electrodes placed on the right and left shoulders, and just below the left rib. The signals from the ECG and two test devices will be sampled a frequency was 1000 Hz, providing a temporal resolution of 1ms.

DEVICE 4: Doppler Ultrasound

A commercial ultrasound device equipped with 11-3 MHz linear array probe will be used. Experimenters will assess blood flow in three cerebral arteries: common carotid, internal carotid, and vertebral.

DEVICE 5: Continuous Wave Near-Infrared Spectroscopy with Spatially Resolved Spectroscopy (cwNIRS-SRS or NIRS)

A continuous, non-invasive system to measure cerebral perfusion. The near-infrared spectroscopy probe used in this protocol emits a single frequency of light (cwNIRS) to monitor relative change in total hemoglobin. Using the spatially-resolved spectroscopy (SRS) technique, cwNIRS can estimate absolute measures of perfusion (e.g. total hemoglobin, tissue saturation index). The cwNIRS-SRS device will be positions on the forehead, approximately 3cm to the right of the center, directly over the eyebrow. An additional probe will be placed over the medial gastrocnemius to observe venous pooling of blood in the lower-limbs. The location of both probes will be marked to ensure identical placement for the next experimental session. The device will be covered with a dark opaque cloth to prevent signal contamination by ambient light as per manufacturer recommendations.

DEVICE 6: ActiGraph

An ActiGraph accelerometer will be distributed to the research participant at the conclusion of the familiarization session along with a sleep journal packet. The subject will be asked to record on the timeline when he/she began to sleep and awaken each day until the conclusion of his/her participation in this study. The device will be worn on the individual's non-dominant wrist according to manufacturer guidelines. The data collected from this device will be used for one purpose:

- Validate the subject's compliance with pre-testing behavioral restrictions for the purpose of internal validity:
 - Waking up at similar times on the mornings of both experimental session

DEVICES 7 & 8: Data Acquisition (PowerLab) and Data Processing (LabChart)

For the TCD and NIBP, devices, data acquisition and processing will be automated using the accompanying software.

[figure not shown]
For the two test devices, the PowerLab data acquisition system (PowerLab 30 series, ADInstruments, CO, USA) will be used to simultaneously acquire signals from each device and from ECG.

LabChart 8 (ADInstruments) will record and process the data acquired using PowerLab. The ECG signal does not require any post-processing, the software filters ensure a distinct R peak. The foot of the pressure waveforms from the NIBP and PPG devices will be identified using a standard second derivative function. Offline, a custom macro will identify the peak of the R wave and the peak of the second derivative of each pressure waveform, then calculate the time between said peaks.

Cognitive Measurement 1: Trails A+B Tests

Test Structure & Application

The Trail-Making Test – Part A, the circles are numbered 1 – 25, and the subject will draw lines to connect the numbers in ascending order. Part B presents numbers and letters placed in a semi-random fixed order, in such a manner to avoid overlapping lines being drawn. The subject will connect 25 encircled numbers and letters in numerical and alphabetical order, alternating between the numbers and letters. For example, the first number “1” is followed by the first letter “A” followed by the second number “2” then second letter “B” and so on²³ Results for both TMT A and B will be reported in seconds.

Cognitive Measurement 2: Verbal Fluency Task

Test Structure		Application	
Tests of verbal fluency evaluate an individual's ability to retrieve specific information within restricted search parameters ²⁴ . The two subtests are (1) semantic fluency, and (2) phonemic fluency. The total number from each test will be summed and equate to the subjects' cognitive performance.		Verbal Fluency Test	
Phonemic fluency		Rapid generation of words beginning with a specific letter. Typically, F, A, and S are used as stimulus letters.	Instructions
Semantic fluency		Rapid generation of words from within a semantic category. "Animal names" and "supermarket items" are commonly used.	
Alternating fluency		Rapid generation of words by alternating between two semantically unrelated categories. "Fruit and furniture" are often used.	
Excluded-letter fluency		Rapid generation of words that do not contain a specified vowel (e.g., the letter "A").	

Cognitive Measurement 3: Memory Recall

Participants will be read word lists from the Hopkins Verbal Learning Test at the rate of 1 word every 2 seconds pre-test and post- cognitive testing period. The Hopkins Verbal Learning test word lists contain 12 words, 4 words from 3 semantic categories.

Cognitive Measurement 4: Brain Fog

Brain fog will be subjectively measured using a modified Borg Rate of Perceived Exertion (RPE) scale as there is no known reliable and valid objective measure of brain fog. This will be administered pre-test and post-cognitive testing period.

Data Reduction

The data collection periods are listed in Table 3. Minute values are noted in **Figure 1** and are expressed relative to the administration of the MAT.

Table 3. Data reduction methods for experimental protocol

Device	Outcomes	CON (min)	SMS (min)	Reduction
VICORDER®	bfPWV	-5, 0, 5, 10, 15, 20, 25	-115, -15, 0, 5, 10, 15, 20, 25	Measures done in triplicate. Closest 2 will be averaged for mean and variance reported
	cfPWV	-5, 25	-115, -15, 25	
	faPWV	-5, 25	-115, -15, 25	
	CBPs	-5, 0, 5, 10, 15, 20, 25	-115, -15, 0, 5, 10, 15, 20, 25	
	Peripheral BPs	-5, 0, 5, 10, 15, 20, 25	-115, -15, 0, 5, 10, 15, 20, 25	
	Augmentation index	-5, 0, 5, 10, 15, 20, 25	-115, -15, 0, 5, 10, 15, 20, 25	
TCD	Brain PWV	Continuous	Continuous	30s selections made by following a
	MCA velocity	Continuous	Continuous	

	Static cerebral autoregulation	Continuous	Continuous	prearranged protocol. Data for the outcome in the time epoch will be averaged and SD will be reported
	Neurovascular coupling	Continuous	Continuous	
NIBP	Baroreflex sensitivity	Continuous	Continuous	30s selections made by following a prearranged protocol. Data for the outcome in the time epoch will be averaged and SD will be reported
	Heart rate variability	Continuous	Continuous	
	Heart rate	Continuous	Continuous	
Ultrasound	Cerebrovascular BF	-5, 25	-120, -5, 20	
NIRS	Cerebral perfusion	Continuous	Continuous	30s selections made by following a prearranged protocol. Data for the outcome in the time epoch will be averaged and SD will be reported
	Tissue saturation index	Continuous	Continuous	
	Venous pooling	Continuous	Continuous	
ActiGraph	Physical activity	Continuous	Continuous	
	Sleep duration	Continuous	Continuous	
Cognitive Tests	Executive Function	25	25	A single score for each cognitive test is received from each participant from each experiential visit

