Participant Inclusion and Exclusion Criteria:	
Inclusion
 
 • Male or female, aged 35 to 59 years 
Exclusion
 
 • Any known cardio-metabolic disorders • Taking medications known to affect cardiovascular function • Report cigarette smoking • Pregnant women
Number of Participants	20
Study Duration	1 year
Study Phases	
Familiarization: to all devices
 
CON: mental stress without prolonged sitting
 
SMS: mental stress with prolonged sitting

Design	Multi-visit randomized crossover trial

Primary & Secondary Outcomes	
Cerebrovascular Primary: Brain PWV Secondary: Executive Function & Neurovascular Coupling
 
Vascular Primary: Brachial-Femoral PWV Secondary: Carotid-femoral PWV, femoral-ankle PWV, augmentation index, central blood pressures (cSBP, cDBP)

Descriptive/ Mechanistic Outcomes	
Cerebrovascular: Cerebral Perfusion Middle Cerebral Artery Velocity Total Brain Blood Flow Static Cerebral Autoregulation
 
Vascular: Peripheral blood pressure Heart rate Baroreflex Sensitivity Heart Rate Variability Total hemoglobin Tissue saturation index Accelerometer

Statistical and Analytic Plan	
All statistical procedures will be completed with SPSS Statistics version 25.0 (SPSS, IN., Durham, NC, USA) and Jamovi v0.9 (Jamovi, UK). The α-level will be set a prior at 0.05 for all statistical procedures. Descriptive statistics and mechanistic outcomes will be collected to compare similarities amongst the sample group and to eliminate the potential for extraneous covariates. Answering the research question will require a linear, multi-level mixed model.

Data and Safety Monitoring Plan	
No participants will be identified in any report or publication of this study. Participants will be identified via identification code for data collection purposes. All electronically collected data will be stored on a computer that only team members Onyen password will allow access to study information. This computer will be located in the Graduate Student Office of the Applied Physiology Laboratory at the University of North Carolina at Chapel Hill. Data analysis procedures will be performed on secure computers within Fetzer Hall, with which password is required to access.

CONTENTS

PROTOCOL SYNOPSIS.....	2
ABBREVIATIONS	7
1 BACKGROUND AND RATIONALE.....	9
Introduction and Rationale.....	9
1.1 Objective(s).....	9
1.2 Aims	9
2 STUDY PROCEDURES	10

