Example Set-up		
 Ensure probe is positioned over the temporal window Apply ultrasound gel to probe and/ or temporal window Move probe until faint trace appears and then make further fine movements to increase trace of artery velocity

Raw Data		
 Signal quality is indicated by color: the more yellow, the stronger the signal Gain and depth adjust can be made in the signal window. Gain should sit between 38-44 for optimal signal output Typical velocities for middle cerebral artery (MCA) are ~80 cm/s-1, and ~60 cm/s-1 in older populations Typical depth for MCA is 45-55
Data Analysis		
 Using a custom macro, the software (Labchart) identifies the peak of the ECG R- wave and the peak of the second derivative of each pressure waveform (corresponds to foot), then calculate the transit time (TT) between said peaks. Pulse wave velocity (PWV) = distance (L) / TT
Data Reduction		
 Measures of brain PWV, MCA velocity, static CA and neurovascular coupling will be collected from this device are continuously recorded during a testing session Data reduction for this protocol will require the selection of 30s epochs at specific time points to observe how PS and MS are impacting measures of CVH In the picture to the left, a researcher selected a time period to report the data collected during this time. A strict protocol will be followed to ensure that selection of 30s epochs are synchronized amongst all measures and research participants to prevent bias.

Device 3: Non-Invasive Blood Pressure (NIBP)

Device		
 Company: ADInstruments Model: Human NIBP Nano System, Finapress Location: Sydney, Australia Single cuff contains an infrared photoplethysmographic (940 mmHg) sensor and inflatable cuff. PPG sensor continuously captures the pulse waveform. Inflatable cuff used to calibrate waveform Height correction unit corrects for hydrostatic pressure changes due to change in hand position relative to the heart.
Example Set-up		
 Device placed between distal and proximal inter-phalangeal joint of the index finger. Wrist apparatus is strapped to the individual's non-dominant wrist
Raw Data		
 Data captured using a data acquisition system (PowerLab). Also displayed are electrocardiogram (ECG) signals captured by PowerLab.

[figure not shown]

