4.2 Statistical Analysis

All statistical procedures will be completed with SPSS Statistics version 25.0 (SPSS, IN., Durham, NC, USA) and Jamovi v0.9 (Jamovi, UK). The α -level will be set a prior at 0.05 for all statistical procedures. Descriptive statistics and mechanistic outcomes will be collected to compare similarities amongst the sample group and to eliminate the potential for extraneous covariates. Answering the research question will require a linear multi-level mixed model. Statistical models will observe for changes in the primary and secondary outcomes within conditions (Baseline, Post-PS, Post-MS) and between conditions (CON vs. SMS at similar time points). Mechanistic outcomes will also be used to assist in discussions of physiological responses to MS and PS. Effect sizes will be calculated as Cohen's d , where <0.20 is considered to be a small, > 0.20 to < 0.50 a moderate, and > 0.60 a large effect. For the mixed models Cohen's d will be calculated as the effect of condition (β) or time (β) from linear mixed models divided by the baseline SD. Raw data will be presented as mean [standard deviation] and mixed model data are presented as mean [95% confidence interval].

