4.3 Tabulation of Results

Mean and variance will be tabulated after raw measures taken in triplicate are entered into a lab-created template.

Table 4. Methods to describe result summarization for this experimental protocol.

Abbreviations: X, Mean/SD will be calculated for this result; 1, Measure is reported as a single value from each experimental visit; n/a, Measure is not being taken at this timepoint.

Device	Outcomes	Baseline		Post-PS		Post-MS	
		X	SD	X	SD	X	SD
VICORDER®	bfPWV	X	X	X	X	X	X
	cfPWV	X	X	X	X	X	X
	faPWV	X	X	X	X	X	X
	CBPs	X	X	X	X	X	X
	Peripheral BPs	X	X	X	X	X	X
	Augmentation index	X	X	X	X	X	X
TCD	Brain PWV	X	X	X	X	X	X
	MCA velocity	X	X	X	X	X	X
	Static cerebral autoregulation	X	X	X	X	X	X
	Neurovascular coupling	X	X	X	X	X	X
NIBP	Baroreflex sensitivity	X	X	X	X	X	X
	Heart rate variability	X	X	X	X	X	X
	Heart rate	X	X	X	X	X	X
Ultrasound	Cerebrovascular BF	1	X	1	X	1	X
NIRS	Cerebral perfusion	X	X	X	X	X	X
	Tissue saturation index	X	X	X	X	X	X
	Venous pooling	X	X	x	X	x	X
Cognitive Tests	Executive Function	n/a	n/a	n/a	n/a	1	X

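### Neurovascular coupling is to be reported at Baseline and Post-PS, where no task is scheduled, so at least those values cannot measure coupling as the plan defines it

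*Combined protocol and SAP*

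**What the plan says.** The synopsis lists the outcome under cerebrovascular function: "Secondary: Executive Function & Neurovascular Coupling". Section 4.1 gives it the same rank.

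Table 2 in Section 2.5 defines it as the "relationship between local neural activity and subsequent changes in cerebral blood flow", calls it unitless, and assigns it to NIRS and TCD together. The definition carries an unfilled citation marker, and no formula follows.

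Table 3 places it with the other TCD measures. The reduction rule for that group begins "30s selections made by following a" prearranged protocol, and continues: "Data for the outcome in the time epoch will be averaged and SD will be reported". Section 3, Device 2, repeats this: "Measures of brain PWV, MCA velocity, static CA and neurovascular coupling will be collected from this device are continuously recorded during a testing session", with a strict protocol so that "selection of 30s epochs are synchronized amongst all measures and research participants to prevent bias".

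Section 4.2 says that the models will look for "changes in the primary and secondary outcomes within conditions (Baseline, Post-PS, Post-MS"), and between conditions at similar times. In Table 4 (Section 4.3) the row "Neurovascular coupling" has a mean and SD in all three columns. The executive function row, by contrast, is marked n/a at Baseline and Post-PS.

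**The concern.** By the plan's own definition, coupling has two parts: local neural activity, and a change in flow that follows it. Measuring it takes a stimulus and a comparison of flow before and during that stimulus. The plan names neither for this outcome. It treats coupling like a level, such as MCA velocity, which can be averaged over 30 s at any time in the visit.

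If the tables are followed as written, values labelled as coupling will be produced at times when nothing is scheduled to evoke neural activity. They will enter the mixed model, and any SMS versus CON difference will be read as an effect of sitting on coupling. With no stated index, there is also room to choose one after the recordings have been seen.

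**Working it through.** No sample size, power or alpha figure is involved (Section 4.1 bases power on PWV). The check compares when tasks are scheduled with when coupling is to be reported.

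**Scheduled tasks**
- Mental arithmetic test: -5 to 0 min, once per visit (Section 2.6, both timelines). The Figure 2 caption sets time zero at completion of the stressor. The Table 2 caption refers only to administration of the test, but the timelines place its end at 0.
- Trails A+B and verbal fluency: 30 to 40 min in the timelines, but 25 min in Tables 2 and 3.
- Word-list recall (Section 2.5, Cognitive Measurement 3): before testing and after the cognitive tests. It has no clock time and is on neither timeline.

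**Reporting points against tasks**

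| Point | Window | Scheduled task in it |
|---|---|---|
| CON, before the arithmetic test | -15 to -5 min (timeline) | none |
| SMS Baseline | -125 to -110 min (timeline) | none |
| SMS Post-PS | -20 to -5 min (timeline) | none |
| Post-MS, 30 s epochs at 0, 5, 10, 15, 20 min | assumed from the VICORDER schedule | none |
| Post-MS, 30 s epoch at 25 min | assumed from the VICORDER schedule | none if the tests start at 30; Trails/fluency if they start at 25 |

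**Baseline and Post-PS.** Continuous recording starts at -15 min in CON and -125 min in SMS. Neither timeline has a task between that start and -5 min, so the result does not depend on where the unseen epoch protocol places these two epochs. Section 2.3 describes the SMS sitting period as quiet viewing of an unstimulating film.

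**Post-MS.** The NIRS examples in Section 3, Device 5, are epochs right after the test and five minutes later. TCD epochs are synchronised across measures, so none appears to be set aside for coupling. Post-MS therefore seems to fall after the task, but this is an inference.

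**The one clear stimulus.** TCD, NIRS and NIBP record through -5 to 0 min, but no column of Table 4 and no level of the Section 4.2 model covers that period.

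**Size**
- If both conditions fill all three columns: 20 participants x 2 visits x 3 columns = 120 values, of which 20 x 2 x 2 = 80 are at Baseline or Post-PS.
- If CON supplies only one pre-test value, as in Table 2's VICORDER rows: 20 x (2 + 3) = 100 values, of which 20 x (1 + 2) = 60 precede the test.
- One task-evoked value per visit would give up to 20 x 2 = 40 values and 20 paired differences.

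**The case against.** The strongest reply is that the plan is incomplete here rather than wrong. Epochs follow a prearranged protocol that is not reproduced, and the schedule figure is not available. Tables 2 and 3 put the cognitive tests at 25 min, so a late Post-MS epoch could overlap them. The word-list task has no clock time and might come before the arithmetic test. All of this stands, and it is why the Post-MS part is only an inference. It does not rescue Baseline and Post-PS. No timeline shows a task there, nothing links the word lists to coupling, and one average over a single epoch is still not a comparison of task with rest.

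A reader might also infer three stronger points that the documents do not support:
- *Table 2's single measurement contradicts Table 4's three time points.* Table 2 gives 1 for every continuously recorded outcome, including heart rate and MCA velocity. It most plausibly means one recording.
- *The outcome merely duplicates MCA velocity and cerebral perfusion.* No formula is given. Table 2 describes a unitless relationship from two devices, so duplication is possible but not shown.
- *The trial can say nothing about coupling.* The recordings run through the arithmetic test, so a task-evoked response can still be derived.

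A last objection concerns the remedy. The arithmetic test is the stressor under study, so a velocity change during it mixes coupling with any blood-pressure response. Neural activity is not measured directly, and Protocol 1 does not record correct answers, so engagement cannot be checked. This stands, and it limits what the derived value may be called.

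**Conclusion.** The point holds for Baseline and Post-PS: two of the three Table 4 columns, 80 of 120 values or 60 of 100 depending on how CON is tabulated, cannot represent coupling as Table 2 defines it. This rests on the session timelines listing every task that could serve as a stimulus. For Post-MS the same conclusion is likely but unproven, since it assumes epochs at the VICORDER times and cognitive tests starting at 30 min.

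This is more than a missing definition, because the stated tabulation and model levels conflict with the stated definition. The outcome is secondary in a study labelled as pilot testing, and the primary PWV outcomes are unaffected. It should be corrected before data reduction.

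**What to change.** 1. In Table 4, and in the Section 4.2 model for this outcome, mark Baseline and Post-PS as n/a, as Table 4 already does for executive function.
2. Derive one value per visit from the continuous record: R = 100 x (MCAv during - MCAv before) / MCAv before. 'Before' is a fixed 30 s epoch just ahead of the arithmetic test and 'during' is a fixed epoch inside it. Both clock times should be written down in advance. Report the prefrontal tHb change over the same epochs beside it. Compare R between SMS and CON within participants.
3. Express the response relative to NIBP mean arterial pressure in the same epochs as well, for example as the change in MCAv/MAP. Call the result a task-evoked cerebrovascular response.
4. If the sponsor does not accept the arithmetic test as the stimulus, relabel the tabulated values as resting TCD/NIRS measures and draw no conclusion about coupling.
5. State whether the cognitive tests start at 25 or 30 min, so that the Post-MS epochs can be placed.

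The cost is plan wording and a different choice of epochs from recordings already planned, with no added visit, device or procedure. The price is a narrower claim: pressure adjustment does not fully separate coupling from stress reactivity, and the pre-test level in the denominator may itself differ after prolonged sitting, so the before and during levels should be shown with R.

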3 MEASUREMENT DEVICES

[figure not shown]
[figure not shown]
Device 1: VICORDER®

Device		
 Company: SMT Medical Model: VICORDER®: Arterial Stiffness Model Location: Wurzburg, Germany Oscillometric cuffs inflate at sub-systolic pressures to detect changes in the pressure waveform. Different sized cuffs are available.
Example Set-up		
 The cuffs can be placed on any 2 arterial segments. In the figure to the left, pressure cuffs placed over the brachial and femoral arteries. A small balloon is placed over the carotid artery to obtain a measurement for cfPWV. A low pressure (50 mmHg) is used for this site with minimal discomfort.
Raw Data		
 Top display = pressure waveform from proximal arterial segment Bottom display = pressure waveform from distal arterial segment Intrinsic software automatically detects the foot of the waveform of each arterial segment
Data Analysis		
 A = Site of proximal artery B = Site of distal artery Pulse wave velocity (PWV) = distance (D) / transit time (TT) Straight line distance (L) = Distance between two cuffs as measured according to manufacturer guidelines

[figure not shown]
[figure not shown]
		
 Transit Time (ΔT or TT) = Time between foot of proximal and distal waveforms. Oscillometric pressure waveforms will be determined at the brachial artery of the non-dominant arm using the VICORDER® in order to determine brachial and central arterial blood pressures.
Data Reduction		
 L is plugged into software prior to measurement. TT is averaged across 3 waveforms, and used to calculate one PWV Process repeated 3 times, for 3 PWVs per measurement cycle. Closest 2 PWVs averaged and used as outcome for measurement cycle.

[figure not shown]
Device 2: Transcranial Doppler (TCD)

Device		
 Company: Compumedics DWL Model: Transcranial Doppler Sonography TCD Location: Charlotte NC, USA DiaMon headset can be adjusted in 3 ways to accommodate each individual Connection between rear band and side panel sits behind the ear, below the occipital bone to ensure signal TCD probes should be in contact with head if headset has been fitted correctly

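### Brain PWV, a primary outcome, is timed from a Doppler signal recorded at 50 Hz against an ECG recorded at 1000 Hz, and the devices meant to share the ECG rate are not named

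*Combined protocol and SAP*

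**What the plan says.** Brain PWV is one of two primary outcomes (section 4.1; Table 2 gives TCD as its device). Section 2.5, DEVICE 2, says: "Brain PWV and Middle cerebral artery velocity (MCAv) will be measured using continuous bilateral TCD", and then: "The data will be acquired continuously (50 Hz) using an analog-to digital convertor (PowerLab 30, ADInstruments".

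DEVICE 3 (the non-invasive blood pressure device, NIBP) says that the ECG and two test devices are "sampled a frequency was 1000 Hz, providing a temporal resolution of 1ms". It does not name the two devices.

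DEVICES 7 & 8 in section 2.5 contains three relevant statements:

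- "For the TCD and NIBP, devices, data acquisition and processing will be automated using the accompanying software".
- A later sentence begins "For the two test devices, the PowerLab data acquisition system" and sends those devices to PowerLab together with the ECG.
- The next paragraph names a different pair: "The foot of the pressure waveforms from the NIBP and PPG devices will be identified using a standard second derivative function".

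In section 3, the Device 2 table defines transit time as the interval from the ECG R-peak to the foot of a waveform, and PWV as path length divided by that time. The example set-up for Devices 7 & 8 shows TCD inputs on the PowerLab unit.

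**The concern.** A transit time is the difference between two time stamps, so it is no more precise than the coarser of the two signals. Here the start point comes from a channel with 1 ms resolution. The end point comes, on the only rate expressly tied to TCD, from a channel with 20 ms resolution. The finer ECG rate then does little for this outcome.

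The recording rate has to be set before the first visit. An operator who follows DEVICE 2 records at 20 ms, and timing detail lost at recording may not be recoverable offline. One who takes TCD to be among the unnamed test devices records at 1 ms. The protocol does not tell them which is intended.

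**Working it through.** **Sampling intervals.** Interval = 1000 / rate in Hz, in ms.
- 1000 Hz: 1000 / 1000 = 1 ms, which reproduces the figure in DEVICE 3.
- 50 Hz: 1000 / 50 = 20 ms, which is 20 times coarser.

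**Timing error per beat.** Rounding to the nearest sample gives an error of at most half an interval, with SD = interval / sqrt(12).
- 50 Hz: up to 10 ms either way, SD 20 / 3.464 = 5.77 ms.
- 1000 Hz: up to 0.5 ms either way, SD 0.289 ms.

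**Timing error per 30 s epoch.** Table 3 reduces TCD data over 30 s selections. Assume 33 beats with independent rounding.
- 50 Hz: 5.77 / sqrt(33) = 1.005 ms (1.155 ms for 25 beats, 0.913 ms for 40).
- 1000 Hz: 0.289 / sqrt(33) = 0.050 ms.

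**Illustrative comparison with a change in PWV.** From section 4.6: an aortic PWV of 7.5 m/s, a change of 1 m/s, a usual error of 1.25 m/s. Assumed, because the documents do not give them: path length L of 0.20-0.50 m, no delay between R-peak and pulse departure, no interpolation between samples, epoch PWV = L / mean transit time.

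Change in transit time = L/7.5 - L/8.5. Added SD of PWV is approximately PWV² / L × 0.001005 s.

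| L (m) | Change in transit time (ms) | 1.005 ms as share of change | Added SD at 7.5 m/s | Added SD at 8.5 m/s |
|---|---|---|---|---|
| 0.20 | 3.14 | 32% | 0.28 | 0.36 |
| 0.30 | 4.71 | 21% | 0.19 | 0.24 |
| 0.50 | 7.84 | 13% | 0.11 | 0.15 |

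Simulation of 20,000 epochs gives the same added SDs to within 0.002 m/s. At 1000 Hz the added SD is at most 0.018 m/s.

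**Illustrative power.** Two-sided 5% paired t test, true difference 1 m/s, total SD = sqrt(paired SD² + the two added SDs²). For L = 0.20 and paired SD 1.25: sqrt(1.5625 + 0.080 + 0.132) = 1.33.

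| Paired SD (m/s) | n | No added error | L = 0.20 | L = 0.30 | L = 0.50 |
|---|---|---|---|---|---|
| 1.25 | 20 | 0.924 | 0.889 | 0.909 | 0.919 |
| 1.25 | 18 | 0.892 | 0.851 | 0.874 | 0.886 |
| 1.77 | 20 | 0.670 | 0.642 | 0.657 | 0.666 |

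The last row applies if 1.25 m/s is the error of each measurement, so that the paired SD is 1.25 × sqrt(2) = 1.77. At 1000 Hz the power is unchanged to three decimals.

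**Which devices are the two test devices?** Two readings are possible.
- TCD and NIBP: this pair is named first in DEVICES 7 & 8, and section 3 shows both feeding PowerLab. TCD would then carry two rates.
- NIBP and PPG: the text gives TCD and NIBP to their own software, then turns to the two test devices, then names NIBP and PPG. TCD would then stay at 50 Hz. Against this, section 3 describes PPG as the sensor inside the NIBP cuff, and it is not a listed device.

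No sentence settles the matter.

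**The case against.** A reader might infer that the protocol contradicts itself by giving TCD both 50 Hz and 1000 Hz. The documents do not establish that. Only 50 Hz is expressly attached to TCD. The 1000 Hz sentence stands under NIBP and does not mention TCD, and the NIBP/PPG reading removes the conflict. A figure that is not reproduced in the available text sits between the key sentences of DEVICES 7 & 8 and might identify the devices. This objection stands, and the fair description is unclear text.

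The numerical consequence can also be challenged. It borrows aortic values for a cerebral measure and assumes a path length. It also ignores any R-peak delay, although section 3 times from the R-peak. With a 100 ms delay, a true 7.5 m/s would appear as 1.6 m/s (0.20 / 0.1267) to 3.0 m/s (0.50 / 0.1667), and a 1 m/s change as about 0.04-0.15 m/s. Power stays at 0.890-0.919 with a delay of 50 or 100 ms, but only if the paired SD is scaled to the apparent change, so that result is no independent support. Nor is the assumed epoch rule in the protocol, since Table 3 can be read as averaging beat-by-beat PWVs. All of this stands, so the power figures are an illustration only.

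Finally, 1000 Hz may gain nothing if the TCD output itself updates slowly. The documents do not give that bandwidth. This stands too, and it is why the fix begins with a check.

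What the objections do not remove is that DEVICE 2, as written, records a primary outcome 20 times more coarsely than the ECG it is timed against.

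**Conclusion.** The point holds as a minor, inexpensive improvement to the measurement specification. DEVICE 2 sets 20 ms resolution for a transit time whose start is resolved to 1 ms, and DEVICE 3 leaves the devices sharing the 1000 Hz rate unnamed.

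Under the stated assumptions, the added error is about 1.0 ms SD per epoch. With 20 participants, power falls by 0.005-0.035 if 1.25 m/s is the paired SD, and by 0.004-0.028 if the paired SD is 1.77. If TCD is in fact recorded at 1000 Hz and its output supports that resolution, the loss is negligible and only the wording needs repair.

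A reader might also infer that brain PWV is unusable or the trial seriously underpowered for it. The figures do not support that: averaging over beats removes most of the random rounding error, and the sample size in section 4.6 rests on aortic PWV.

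**What to change.** 1. Before the first visit, check whether the TCD analogue output carries timing finer than 20 ms.
2. If it does, state in section 2.5, DEVICE 2, that the TCD channel used for brain PWV is recorded at 1000 Hz, the same as the ECG. If it updates no faster than every 20 ms, keep the lower rate and state the true timing resolution of brain PWV.
3. In DEVICE 3, name the two test devices, and use the same names in DEVICES 7 & 8.

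The cost is a few sentences, one channel setting, larger files and one bench check.

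Three neighbouring items are separate clarifications and add no weight to this point:
- DEVICE 2 in section 2.5 names a Spencer Technologies TCD system, while the section 3 table gives "Company: Compumedics DWL".
- The Device 2 table in section 3 does not say which pressure waveform is timed for a device that measures velocity.
- The epoch rule for brain PWV could be written as path length over mean transit time, in line with the VICORDER rule that "TT is averaged across 3 waveforms, and used to calculate one PWV".
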